8.3 Adverse Events (AEs), Serious Adverse Events (SAEs), and Other Safety Reporting

The definitions of an AE or SAE can be found in Appendix 3: Adverse Events: Definitions and Procedures for Recording, Evaluating, Follow-up, and Reporting.

AEs will be reported by the participant (or, when appropriate, by a healthcare provider, caregiver, surrogate, or the participant's legally authorized representative). The investigator and any qualified designees are responsible for detecting, documenting, and recording events that meet the definition of an AE or SAE and remain responsible for following up AEs that are serious, considered related to the study intervention or study procedures, or that caused the participant to discontinue the trial.

Adverse events of special interest (AESIs) include any AEs which occur within 2 hours of end of study drug infusion and which fall under the standardized MedDRA queries of "Angioedema", "Anaphylactic reaction", and "Anaphylactic shock" as well as a list of MedDRA terms relating to "Hypotension".

The method of recording, evaluating, and assessing causality of AEs, AESI and SAEs and the procedures for completing and transmitting SAE reports are provided in Appendix 3.

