9.3.2.2 Outcome Analysis for 1-Year Sub-Study

The outcomes of the 1-Year Sub-Study are intended to be supportive of the 90-day outcomes of the main study. The analysis population will be comprised of participants with a valid consent for the 1-year sub-study in the relevant jurisdiction. Missing data will be imputed as per Section 9.3.1. A summary table will specify the differences between the population analyzed in the main study and the 1-year sub-study, including deaths, losses to follow-up and withdrawal of consent.

The primary outcome is the proportion of subjects with independent functioning on the modified Rankin Scale (mRS), as defined by a score of 0-2) at 1 year.

The secondary outcomes include:

- A reduction in mortality rate, as defined by event rate (%) for mortality over the 1-year study period.
- The proportion of subjects with independent function on activities of daily living defined on the modified Barthel Index (BI) with a score of \geq 95 at 1 year.
- Health-related quality of life, as measured by the EQ-5D-5L at 1 year.

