13.2 Assessment Questionnaires

Below is a sample of the assessment questionnaires and instructions to be used in the trial.

Modified Rankin Scale (mRS)	Clinician Reported Outcome
	English example
National Institute of Health Stroke Score	Clinician Reported Outcome
(NIHSS)	English example.
Barthel Index	Clinician Reported Outcome
	English example.
EQ-5D-5L	Patient Reported Outcome
	USA, English Interviewer Administered example
	See https://euroqol.org/ for device, country, and language specific versions

Statistical Analysis Plan

A Multicentre, Randomized, Double-blinded, Placebo-controlled, Parallel Group, Single-dose Design to Determine the Efficacy and Safety of Nerinetide in Subjects with Acute Ischemic Stroke Undergoing Endovascular Thrombectomy Excluding Thrombolysis

(ESCAPE-NEXT Trial)

Protocol NA-1-009

Product:	Nerinetide
IND:	118,087
Sponsor:	NoNO Inc. [name]
Date	18 November 2021
Version	Final 2.0

SIGNATURES OF APPROVAL

Personal Protected Data

Version History

This Statistical Analysis Plan (SAP) for the trial ESCAPE-NEXT is based on Protocol V5.0, dated 18 November 2021.

Version	Date	Change	Rationale
1.0	03 May 2021	Not Applicable	Original version
2.0	18 Nov 2021	- Updated hierarchical testing order of secondary endpoints: moved the NIHSS responder endpoint to the last.	 The change in testing order of NIHSS endpoint was due to the concern of increased missingness of Day 90 NIHSS scores that may impact statistical power. NIHSS cannot be conducted over the phone. Due to COVID-19 there is an increase in the number of Day 90 visits being conducted by phone.
		 Updated the primary analysis model for all binary efficacy endpoints: a generalized linear regression model with adjustment for baseline covariates and randomization stratification factor will be used Changed one of supportive analyses of the primary efficacy endpoint to an unadjusted logistic regression Added robust estimation of unconditional treatment effect for the primary efficacy endpoint analysis 	- The updates in primary analysis model as well as the addition of unconditional treatment effect were made to be aligned with the FDA draft guidance "Adjusting for Covariates in Randomized Clinical Trials for Drugs and Biological Products" dated in May 2021

TABLE OF CONTENTS

SIGNATURES OF APPROVAL		
Version History		
Table of Contents		
List of Tables		
1 Introduction		

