6.6 Outcome Analysis for 1-Year Sub-Study

The outcomes of the 1-Year Sub-Study are intended to be supportive of the 90-day outcomes of the main study. The analysis population will be comprised of participants with a valid consent for the 1-year sub-study in the relevant jurisdiction. Missing data will be imputed as per Section 4.3 except that for subjects who are successfully contacted (i.e., not deceased) but who cannot complete the telephone interview (e.g., due to dysphasia, a language barrier, or incapacity) will have their outcomes estimated by the interviewer. A summary table will specify the differences between the population analyzed in the main study and the 1-year sub-study, including deaths, losses to follow-up and withdrawal of consent.

The primary outcome is the proportion of subjects with independent functioning on the modified Rankin Scale (mRS), as defined by a score of 0-2) at 1 year.

The secondary outcomes include:

- A reduction in mortality rate, as defined by event rate (%) for mortality over the 1-year study period.
- The proportion of subjects with independent function on activities of daily living defined on the modified Barthel Index (BI) with a score of \geq 95 at 1 year.
- Health-related quality of life, as measured by the EQ-5D-5L at 1 year.

6.6.1 mRS at 1 Year

The mRS will be assessed as per the protocol. It will be dichotomized, analyzed and reported as in the primary efficacy analysis.

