6.6.4 EQ-5D-5L at 1 Year

The EQ-5D-5L will be obtained by telephone or in-person interview from trial participants at 1 year. EQ-5D-VAS will be analyzed and reported as described in Section 6.3.5.

Table 4: Summary of Inferential Efficacy Analyses

	Endpoint	Primary Analysis*	Sensitivity Analysis*	Supportive Analysis*
Primary	Day-90 mRS Responder (≤2 vs. >2)	Adjusted log-binomial regression model, ITT, SI Estimation of unconditional treatment effect will also be reported.	 Adjusted log-binomial regression model, ITT, OC Adjusted log-binomial regression model, ITT with Day 90 completers only (if missingness ≤ 5%) Adjusted log-binomial regression model, ITT, MI (if missingness > 5%) Adjusted log-binomial regression model, ITT, Tipping Point Analysis (if missingness > 5%) 	 Primary analysis with the interaction term added (treatment by randomization stratification factor) Adjusted log-binomial regression model, ITT, Re-randomization CMH, ITT, SI Unadjusted logistic regression, ITT, SI Adjusted log-binomial regression model, PP, OC
Secondary	Day-90 Mortality	Adjusted log-binomial regression model, ITT Missing data imputed based on Day 30 status	Adjusted log-binomial regression model, ITT, OC	 Mortality Rate: Unadjusted logistic regression, ITT, Missing data imputed based on Day 30 status Adjusted log-binomial regression model, PP, OC Time to Death (Days): Kaplan Meier, ITT, OC Cox proportional hazard regression, ITT, OC
	Worsening of Stroke	Adjusted log-binomial regression model, ITT, Missing data imputed based on Day 30 status	Adjusted log-binomial regression model, ITT, OC	 Unadjusted logistic regression, ITT, Missing data imputed based on Day 30 status Adjusted log-binomial regression model PP, OC
	Day-90 mRS shift (Ordinal)	POM, ITT, SI	POM, ITT, OCPOM, ITT with Day 90 completers only	POM, PP, OC
	Day-90 NIHSS Responder (≤2 vs. >2)	Adjusted log-binomial regression model, ITT, LOCF	Adjusted log-binomial regression model, ITT, OC	 Unadjusted logistics regression, ITT, LOCF Adjusted log-binomial regression model, PP, OC
Tertiary	Stroke volume	Linear regression, ITT, OC	N/A	Student's t-test, ITT, OC
	Day-90 Barthel Responder (<95 vs.≥95)	Adjusted log-binomial regression model, ITT, OC	N/A	N/A
	Day-90 mRS	Adjusted log-binomial	N/A	N/A

	Endpoint	Primary Analysis*	Sensitivity Analysis*	Supportive Analysis*
	Responder (≤3 vs. ≥4)	regression model, ITT, SI		
	Day-90 mRS Responder (≤1 vs. >1)	Adjusted log-binomial regression model, ITT, SI	N/A	N/A

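### SAP 6.6 has the interviewer estimate 1-year outcomes for participants who cannot complete the call, with no exception for the self-rated EQ-VAS, no required information source and no flag

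*Combined protocol and SAP*

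**What the plan says.** The rule is one sentence in SAP 6.6. It opens "Missing data will be imputed as per Section 4.3 except that for subjects who are successfully contacted" and goes on to those who cannot complete the telephone interview: "e.g., due to dysphasia, a language barrier, or incapacity) will have their outcomes estimated by the interviewer". The same section lists the 1-year outcomes as mRS 0-2, mortality, Barthel Index of at least 95, and "Health-related quality of life, as measured by the EQ-5D-5L at 1 year". The rule is not restricted to any of them.

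Other places that bear on it:

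- **Type of instrument.** Protocol 13.2 lists mRS, NIHSS and Barthel as clinician-reported and EQ-5D-5L as "Patient Reported Outcome". Protocol 8.1.7 and SAP 3.7 have respondents rate their own health from 0 to 100.
- **Stated source.** SAP 6.6.4 says "The EQ-5D-5L will be obtained by telephone or in-person interview from trial participants at 1" year. SAP 6.6.3 likewise takes Barthel from participants.
- **Analysis.** SAP 6.6.4 adds that "EQ-5D-VAS will be analyzed and reported as described in Section 6.3.5", which is an ANCOVA. In SAP Table 4, 1-year EQ-VAS is analysed on observed cases and 1-year mRS with multiple imputation. The sensitivity and supportive columns read N/A for every 1-year row.
- **Protocol.** Section 9.3.2.2 says only "Missing data will be imputed as per Section 9.3.1" and has no interviewer exception. Protocol 9.3 gives the SAP precedence where the two differ.
- **Informants elsewhere.** SAP 6.6.2 takes 1-year mortality from family, a representative or hospital records. Protocol 8.3 accepts adverse event reports, "when appropriate, by a healthcare provider, caregiver, surrogate, or the participant's legally authorized representative".

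**The concern.** A 0-100 rating of one's own health cannot be supplied by someone else without becoming a different measurement. If the interviewer fills it in, the value has unknown error and looks in the dataset like any self-rating.

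For mRS and Barthel a trained rater's judgement is the normal mode of scoring, so the rule is less irregular. What is missing is any statement of what the judgement rests on. The language example shows this best: a language barrier is not a disability, and a participant who is functioning well could have mRS and Barthel estimated when an interpreter would have given real answers.

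The reasons for non-completion also matter. Dysphasia and incapacity go with worse outcome, so the estimated values are not a random subset. Neither document flags them, counts them by arm, or analyses the data without them. A reader of the 1-year report could not tell how much of it was estimated.

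**Working it through.** **No plan figure to reproduce.** The documents give no sample size, power or expected non-completion rate for the 1-year sub-study. The 91.3% power in Protocol 9.1 is for Day 90 and is not an input here. The main check is therefore textual.

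**Step 1: is an estimated value missing or observed?** SAP 6.6 frames estimation as an exception to imputation, so an estimated value is not missing. SAP 4.3.2 sends only missing 1-year mRS values to multiple imputation, so an estimated mRS stays as entered. SAP 6.1.3 defines observed cases as an analysis without imputation, so an estimated EQ-VAS would enter it.

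**Step 2: does the rule reach EQ-VAS?** By its wording, yes, since the outcomes are unrestricted and EQ-5D-5L is on the list. SAP 6.6.4 points the other way, because it takes the instrument from participants. The two sections are not reconciled.

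**Step 3: which outcomes are affected in practice?** mRS, Barthel and EQ-5D-5L. Vital status needs no estimate in someone who has been reached.

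**Step 4: how many might be affected? (illustration)** Protocol 2.1.5 gives a 7.5-point absolute and 39.7% relative mortality reduction in the no-alteplase participants of the previous trial.

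- Placebo mortality = 7.5 / 0.397 = 18.9%. Nerinetide mortality = 18.9 − 7.5 = 11.4%. The average is about 15%.
- Survivors of the protocol's 850 = 850 × 0.85 = about 720. This uses Day 90 mortality, so 1-year survivors would be somewhat fewer.
- If 5% to 15% of survivors could not complete a call (an assumption), that is 36 to 108 people.
- If that mortality difference recurred with 425 per arm, survivors would be 425 × 0.886 = 377 and 425 × 0.811 = 345, a gap of 32. Equal numbers of estimated values per arm therefore cannot be taken for granted. The same section reports no increase in severe disability, so an imbalance is a possibility and not a prediction.

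**Step 5: what might it do to the results? (illustration)** Suppose a fraction f of participants in each arm has an estimated mRS class, with sensitivity and specificity both equal to a, the same in each arm. Suppose also that the true difference among them equals the overall difference. Then

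observed difference = true difference × [(1 − f) + f(2a − 1)].

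Taking the Day 90 design difference of 11.4 points as a stand-in:

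| f | number of 850 | a = 0.7 | a = 0.9 |
|---|---|---|---|
| 5% | about 42 | 11.1 | 11.3 |
| 10% | 85 | 10.7 | 11.2 |
| 20% | 170 | 10.0 | 10.9 |

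For EQ-VAS, if the estimates carried no treatment signal, the mean difference would shrink by the factor 1 − f: 0.95 at 5%, 0.90 at 10% and 0.80 at 20%.

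**Step 6: would deleting the rule be enough?** No. Without it, a missing 1-year Barthel takes the trial median under SAP 4.3.3. If that median is 95 or more (an assumption), a severely disabled non-completer becomes a responder. Missing mRS would go to multiple imputation under missing at random, which is doubtful when disability is the reason for non-completion.

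**The case against.** The best defence has four parts.

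- **mRS and Barthel are rated by trained staff** and analysed as dichotomies (0-2; at least 95). For an incapacitated participant the exact score will seldom change the class. This stands, apart from the language case and participants with dysphasia near the mRS cut-off.
- **The SAP never says in terms that EQ-VAS is estimated and counted as observed.** Under SAP 6.6.4 an unobtainable EQ-VAS might simply stay missing. That is a fair reading, but the literal text of SAP 6.6 says otherwise and the plan does not choose between them.
- **SAP 6.6 does not forbid asking a caregiver.** True, but it does not require it, and it does not record whether it was done.
- **Raters are blinded (SAP 1.7.1) or firewalled (SAP 1.7.2)**, so errors should be similar in the two arms, and the sub-study is supportive. This stands and limits the weight of the point.

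A reader might also infer from the firewall that the interviewer is a stranger to the participant. The documents do not support that. SAP 1.7.2 separates interviewers from the sponsor, the IDMC, the unblinded statistician and the coordinating investigators, while Protocol 6.3.1 expects site staff to make the assessments and stay blinded until the 1-year lock.

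**Conclusion.** The point holds in a limited form. As written, SAP 6.6 allows an interviewer-made EQ-VAS into an observed-case analysis of a self-rated measure, against Protocol 13.2 and SAP 6.6.4. For mRS and Barthel the gap is the absence of a required information source. For all three, no flag, count by arm or sensitivity analysis would reveal the extent.

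The size cannot be taken from the documents. Under the stated assumptions, with 10% of participants affected, an 11.4-point mRS difference would appear as 10.7 to 11.2 points, and an EQ-VAS difference would keep 90% of its size if the estimates carried no signal. Both results assume similar error and similar numbers affected in each arm.

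It would go too far to conclude that the 1-year results are biased towards one arm, or that every 1-year outcome is guesswork. Blinding argues against the first and clinician rating of mRS and Barthel against the second. Day 90 analyses do not use this rule, and no 1-year outcome is in the fixed testing sequence of SAP 4.1. The change is worth making because it is cheap and mRS 0-2 is the sub-study's primary outcome.

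**What to change.** Amend SAP 6.6 as follows.

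1. EQ-5D-5L and EQ-VAS are never estimated by the interviewer. If the participant cannot answer, the value is missing under the planned observed-case analysis. If a caregiver or representative answers as proxy, the value is flagged and kept out of the main EQ-VAS analysis. Protocol 13.2 mentions device, country and language versions of the questionnaire but no proxy version, so the proxy route should be optional.
2. mRS and Barthel are scored by the trained, blinded rater with a caregiver or representative as informant, or through an interpreter where language is the obstacle. With no informant, the rater's score is kept and flagged as estimated. Barthel is not sent to the median imputation of SAP 4.3.3.
3. Estimated and proxy values are counted by arm, and the 1-year mRS and Barthel analyses are repeated without the estimated values.
4. SAP 6.6, SAP 6.6.3, SAP 6.6.4 and Protocol 9.3.2.2 are aligned so that all four give the same rule.

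The cost is some wording, a source field on the 1-year form, a few more missing EQ-VAS values and a small amount of extra analysis.

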6.6.2 Mortality Rate at 1 Year

Mortality at 1 year will be assessed as per the protocol (from family or legally authorized representative or from hospital records). It will be analyzed and reported as described in Section 6.2.1.

6.6.3 Barthel Index at 1 Year

The Barthel Index will be obtained as per the protocol from trial participants at 1 year. It will be dichotomized, analyzed and reported as for the primary analysis.

6.6.4 EQ-5D-5L at 1 Year

The EQ-5D-5L will be obtained by telephone or in-person interview from trial participants at 1 year. EQ-5D-VAS will be analyzed and reported as described in Section 6.3.5.

Table 4: Summary of Inferential Efficacy Analyses

	Endpoint	Primary Analysis*	Sensitivity Analysis*	Supportive Analysis*
Primary	Day-90 mRS Responder (≤2 vs. >2)	Adjusted log-binomial regression model, ITT, SI Estimation of unconditional treatment effect will also be reported.	 Adjusted log-binomial regression model, ITT, OC Adjusted log-binomial regression model, ITT with Day 90 completers only (if missingness ≤ 5%) Adjusted log-binomial regression model, ITT, MI (if missingness > 5%) Adjusted log-binomial regression model, ITT, Tipping Point Analysis (if missingness > 5%) 	 Primary analysis with the interaction term added (treatment by randomization stratification factor) Adjusted log-binomial regression model, ITT, Re-randomization CMH, ITT, SI Unadjusted logistic regression, ITT, SI Adjusted log-binomial regression model, PP, OC
Secondary	Day-90 Mortality	Adjusted log-binomial regression model, ITT Missing data imputed based on Day 30 status	Adjusted log-binomial regression model, ITT, OC	 Mortality Rate: Unadjusted logistic regression, ITT, Missing data imputed based on Day 30 status Adjusted log-binomial regression model, PP, OC Time to Death (Days): Kaplan Meier, ITT, OC Cox proportional hazard regression, ITT, OC
	Worsening of Stroke	Adjusted log-binomial regression model, ITT, Missing data imputed based on Day 30 status	Adjusted log-binomial regression model, ITT, OC	 Unadjusted logistic regression, ITT, Missing data imputed based on Day 30 status Adjusted log-binomial regression model PP, OC
	Day-90 mRS shift (Ordinal)	POM, ITT, SI	POM, ITT, OCPOM, ITT with Day 90 completers only	POM, PP, OC
	Day-90 NIHSS Responder (≤2 vs. >2)	Adjusted log-binomial regression model, ITT, LOCF	Adjusted log-binomial regression model, ITT, OC	 Unadjusted logistics regression, ITT, LOCF Adjusted log-binomial regression model, PP, OC
Tertiary	Stroke volume	Linear regression, ITT, OC	N/A	Student's t-test, ITT, OC
	Day-90 Barthel Responder (<95 vs.≥95)	Adjusted log-binomial regression model, ITT, OC	N/A	N/A
	Day-90 mRS	Adjusted log-binomial	N/A	N/A

	Endpoint	Primary Analysis*	Sensitivity Analysis*	Supportive Analysis*
	Responder (≤3 vs. ≥4)	regression model, ITT, SI		
	Day-90 mRS Responder (≤1 vs. >1)	Adjusted log-binomial regression model, ITT, SI	N/A	N/A
	Day 90 EQ-VAS	ANCOVA, ITT, OC	N/A	N/A
1 Year	mRS Responder (≤2 vs. >2)	Adjusted log-binomial regression model, ITT, MI	N/A	N/A
	Day-90 Mortality	Adjusted log-binomial regression model, ITT, OC	N/A	N/A
	Barthel Index	Adjusted log-binomial regression model, ITT	N/A	N/A
	EQ-VAS	ANCOVA, ITT, OC	N/A	N/A

*For analyses using the adjusted log-binomial regression model, a Poisson model with robust variance will be used if the log-binomial model fails to converge

7 SAFETY ANALYSES

The safety population will consist of all subjects who received any dose of study drug. The main analyses will be frequency of SAEs and 90-day mortality. It is expected that the safety population and the ITT population will be near-identical.

7.1 Adverse Events

Additional analyses will consider the frequency of AEs and discontinuations due to AEs.

AEs will be collected until Day 30 and SAEs will be collected until Day 90 or the final contact. AEs will be summarized by presenting, for each treatment group, the number and percentage of subjects having at least one AE, having an AE in each body system and preferred term, by severity and relatedness to study medication. The frequencies and incidences of AEs occurring in subjects in the drug and placebo control groups will be summarized within treatment group by the Medical Dictionary for Regulatory Activities (MedDRA) System Organ Class (SOC). The frequencies and incidences of discontinuations due to AEs occurring in subjects in the nerinetide and placebo control groups will be summarized within treatment group.

If a given subject had more than one AE mapped to the same preferred term, then that subject will be counted only once within that preferred term.

A listing of Adverse Events of Special Interest (AESIs) can be found in Appendix 9.1

When reporting TEAEs by maximum severity, if a given subject had more than one AE mapped to the same preferred term, then that AE will be counted once according to the maximal level of severity (Severe, Moderate, Mild).

When reporting TEAEs by relationship to study treatment, if a given subject had more than one AE mapped to the same preferred term, then that AE will be counted once according to the highest level of relatedness (Related, Possibly, Unrelated).

The following summaries (tables) of AEs and TEAEs will be provided by number (percentage) of subjects for each treatment group:

- Overview of Adverse Events
- TEAEs (with a start date 0-30 days) by MedDRA SOC and preferred term
- Serious TEAEs (with start date 0-90 days) by MedDRA SOC and by preferred term
- All TEAEs resulting in death by MedDRA SOC and by preferred term
- Event rate (%) for Serious TEAEs over the 90-day study period between nerinetide and placebo control subjects will be compared by a logistic regression model similar to that of the primary analysis.
- All TEAEs occurring in at least 5% of subjects in either treatment arm, by MedDRA SOC and by preferred term.
- All TEAEs by maximum severity (Severe, Moderate, Mild) by MedDRA SOC and by preferred term. Missing severity grades will be assumed as 'severe'.
- All TEAEs by relationship to study treatment (Related, Possibly, Unrelated) by MedDRA SOC and by preferred term. Missing relationships will be assumed as 'related'.

- Serious TEAEs (with start date 0-90 days) by relationship to study treatment (Related, Possibly, Unrelated) by MedDRA SOC and by preferred term. Missing relationships will be assumed as 'related'.
- All TEAEs resulting in discontinuation of treatment, by MedDRA SOC and by preferred term
- TEAESIs (onset 0-120 minutes post end of study drug infusion and of special interest as defined in Appendix 1: Listing of Treatment-Emergent AEs of Special Interest (TEAESI)) by MedDRA SOC and by preferred term

The following listings of AE occurrences will be provided:

- All AEs by MedDRA SOC and by preferred term
- All SAEs by MedDRA SOC and by preferred term
- All TEAEs leading to death by MedDRA SOC and by preferred term
- All SAEs related to study drug by MedDRA SOC and by preferred term "Related" will include Related, Possibly and missing relationship
- All TEAESIs by MedDRA SOC and by preferred term
- All TEAEs resulting in discontinuation of treatment

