The results of the safety analysis from the ESCAPE-NA1 trial indicate that nerinetide was well tolerated when given as a single IV dose of 2.6 mg/kg with most adverse events occurring with a similar frequency in the drug and placebo groups. The only exception to that was an increase in serous hypotension immediately (within 2 hours) following the administration of nerinetide (6 SAEs in nerinetide vs. 0 in placebo). These cases were reported resolved within 2 days. There were no other differences in other important safety outcomes observed. When nerinetide is administered without alteplase there were fewer deaths and a fewer number of neurological serious adverse events (including stroke in evolution, ischemic stroke and hemorrhagic transformation). When nerinetide is administered with alteplase there were no differences in important safety outcomes observed.

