2.3.1 Risk Assessment

Based on the clinical data available for nerinetide to date, the major possible risk for the proposed use is:

- Higher rate of (transient) hypotension due to a transient elevation of blood histamine
- Effect modification by prior use of alteplase

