9.3 Statistical Analysis

The statistical analysis plan will be finalized prior to any interim analysis and it will include a more technical and detailed description of the statistical analyses described in this section. In the event that there are any inconsistencies between this protocol and the statistical analysis plan, the statistical analysis will be conducted as per the statistical analysis plan. This section is a summary of the planned statistical analyses of the most important estimand endpoints including primary and key secondary endpoints.

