1.8 Definitions

Baseline: A subject's baseline value for a given endpoint or parameter is defined as his/her latest measurement taken prior to study drug administration.

Prior and Concomitant Medications: Prior medications are defined as those taken within 24 hours prior to randomization. Concomitant medications are defined as those taken during study drug administration or after study drug has been administered through to Day 6 (or discharge). All prior and all concomitant medications will be recorded on the electronic case report form.

Randomization: The time of randomization is defined as the time randomization occurred on the central server and this time is considered time zero for the study. All time windows are calculated from the time of randomization.

Study Day: Day 1 is the date of randomization. As the study drug is intended to be administered as soon as possible after randomization (i.e., 15 minutes), this will also be the day of treatment initiation date. Study day is calculated relative to Day 1.

Treatment-Emergent Adverse Event: All AEs will be collected from the start of study drug administration until Day 30. All SAEs will be collected from the start of study drug administration until Day 90. A treatment-emergent adverse event (TEAE) is one that first occurs or worsens in severity or frequency after study drug administration has begun through to and including the Day 30. SAEs are collected through the last study visit. Those AEs that start at the same time and date as the study drug administration and those that first occur or worsen after the start of study drug administration will be considered TEAEs.

AEs with partial or missing dates will be handled as follows:

- If the start day and/or month of the AE is missing the AE will be considered treatmentemergent.
- If the start date is completely missing then the AE will be considered treatment-emergent.

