9 SUPPORTING DOCUMENTATION

Appendix 1: Listing of Treatment-Emergent AEs of Special Interest (TEAESI) 9.1

Table A-1: AEs Related to Angioedema (by preferred term) based on SMQ

Table A-1. Alls Kelateu to Angloeuenna (by p	
Allergic oedema	Auricular swelling
Angioedema	Breast oedema
Circumoral oedema	Breast swelling
Conjunctival oedema	Choking
Corneal oedema	Choking sensation
Epiglottic oedema	Drug hypersensitivity
• Eye oedema	• Ear swelling
• Eye swelling	Endotracheal intubation
Eyelid oedema	Generalised oedema
• Face oedema	Hypersensitivity
Gingival oedema	Laryngeal obstruction
Gingival swelling	Localised oedema
Idiopathic angioedema	Nasal oedema
Idiopathic urticaria	Nipple oedema
Laryngeal oedema	Nipple swelling
Laryngotracheal oedema	• Oedema
Limbal swelling	Oedema mucosal
• Lip oedema	Oedema peripheral
• Lip swelling	Orbital oedema
Mouth swelling	Peripheral swelling
Oedema mouth	Reversible airways obstruction
Oropharyngeal oedema	Skin oedema
Oropharyngeal swelling	Skin swelling
Palatal oedema	• Stridor
Palatal swelling	Suffocation feeling
Periorbital oedema	Throat tightness
Pharyngeal oedema	Tracheal obstruction
Scleral oedema	Tracheostomy
Swelling face	Upper airway obstruction
Swollen tongue	Urticaria
Tongue oedema	• Wheezing
Tracheal oedema	
Table A-2: AEs related to Hypotension (by p	referred term) based on MedDRA Terms
Blood pressure abnormal	Blood pressure orthostatic decreased
Blood pressure decreased	Blood pressure systolic abnormal
Blood pressure diastolic abnormal	Blood pressure systolic decreased
Blood pressure diastolic decreased	Blood pressure systolic inspiratory decreased
Blood pressure difference of extremities	Labile blood pressure
Blood pressure fluctuation	• Hypotension
Blood pressure immeasurable	Diastolic hypotension
Blood pressure inadequately controlled	Hypotensive transfusion reaction

- Hypotensive transfusion reaction •
- Blood pressure orthostatic abnormal Orthostatic Hypotension •

Table A-3: AEs related to Anaphylactic reaction and Anaphylactic shock (by preferred term) based on SMQs

Anaphylactic reaction Anaphylactic shock	
 Anaphylactic reaction Anaphylactic reaction Anaphylactic shock Anaphylactic transfusion reaction 	Anaphylactic shock Acute kidney injury Acute respiratory failure Asthma

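### SAP 7.1 starts the special-interest adverse event window at the end of infusion, so a listed reaction that begins during the infusion is left out of that summary table

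*Combined protocol and SAP*

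**What the plan says.** The last table item in SAP 7.1 summarises special-interest events by system organ class and preferred term, restricted to "TEAESIs (onset 0-120 minutes post end of study drug infusion" and to the terms in SAP Appendix 1. That appendix lists preferred terms for angioedema, hypotension and anaphylaxis, and gives no time window. A separate listing item in SAP 7.1 reads "All TEAESIs by MedDRA SOC and by preferred term" and states no window either.

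The general definition of treatment emergence in SAP 1.8 starts earlier. It covers events that begin at the time of dosing and those that "first occur or worsen after the start of study drug administration will be considered TEAEs".

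Protocol 8.3 defines special-interest events as "any AEs which occur within 2 hours of end of study drug infusion" that fall under the named term groups. It gives an upper limit and no lower one. Protocol 9.3 says that if protocol and SAP are inconsistent, "the statistical analysis will be conducted as per the statistical analysis plan".

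Protocol 6.2 sets the infusion at 10±1 minutes. Protocol 6.4 and 6.8.1.1 let the investigator terminate it at discretion.

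**The concern.** The table exists to show acute reactions to dosing, and protocol 2.3.1 names such a reaction as a major possible risk: "Higher rate of (transient) hypotension due to a transient elevation of blood histamine". A reaction of this kind can begin while the drug is still running in. A programmer who follows SAP 7.1 to the letter would compute onset minus end of infusion and drop any negative value.

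The omission is also selective. A reaction severe enough to make the investigator stop the infusion has, by definition, begun before the infusion ended. It can never fall inside the window, although it is just what a reader would look for in this table.

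At stake is the completeness of the only adverse event table in SAP 7.1 with an onset window measured in minutes around dosing. No efficacy result, error rate or stopping rule depends on it.

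**Working it through.** The plan states no figure that could be reproduced here. The check compares definitions, with some simple counting.

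**1. Place the windows on one clock.** Let the infusion start at minute 0 and end at minute T, with T = 10 as planned.

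| Rule | Lower limit | Upper limit |
|---|---|---|
| Treatment-emergent (SAP 1.8) | 0 | Day 30 |
| Special-interest event (protocol 8.3) | not stated | T + 120 = 130 |
| Special-interest table (SAP 7.1) | T = 10 | T + 120 = 130 |

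**2. Test onsets against the SAP 7.1 table.**
- Onset at minute 5: 5 − 10 = −5, which is below 0. The event is treatment-emergent but not in the table.
- Onset at minute 10, exactly at the end: 10 − 10 = 0. It is in the table.
- A reaction with onset s that causes the infusion to be stopped at e: s < e, so s − e < 0 for every such event. It is never in the table.

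**3. Look for a passage that restores these events to the table.** SAP Appendix 1 defines terms only. Protocol 8.3 is compatible with including the infusion but does not say so. No other section of either document adds them.

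**4. Count what is affected.** SAP 7.1 has 11 adverse event table items, and one, the special-interest table, has a window in minutes. The main event table uses 0 to 30 days and the serious-event table 0 to 90 days. SAP 8.2 sends five safety tables to the IDMC: overview, all events, serious events, events resulting in death, and events resulting in discontinuation. None is the special-interest table.

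**5. Trace where an infusion-time event still appears.** It is in the all-event, severity and relatedness tables and in the listing of all adverse events. If serious, it is also in the serious-event outputs. If it ended treatment, it is in the discontinuation table and listing. The serious-event and discontinuation tables also go to the IDMC.

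**6. Check whether blood pressure data fill the gap.** The schedule in both documents, with its note on infusion-related readings, gives blood pressure immediately before infusion, at its completion, at Visit 2 after the procedure (about 2 hours) and at Day 2/3. SAP 7.2 summarises all of these, and protocol 9.3.3 adds an analysis of the maximum deviation to Day 2. No reading is scheduled during the infusion, and blood pressure readings do not capture angioedema or anaphylaxis.

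**7. Size.** The count of missed events would need onset times relative to dosing. The documents give none.

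**The case against.** The best reply is that the intent is plain. Protocol 8.3 can be read to cover the infusion, and the SAP wording may be no more than loose drafting of the same idea. The precedence clause is also not decisive. SAP version 2.0 says it is based on Protocol V5.0 and describes 680 to 1020 participants with an interim at 75% information, whereas the supplied protocol has up to 850 participants and an interim at 60%. The clause is therefore supporting evidence only. This stands as a limit on which text controls, but it does not put the events into the table, since neither document does so expressly.

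The second reply is that little is lost in practice. The first scheduled blood pressure after dosing begins is at completion of the infusion, so hypotension first detected and dated at that reading falls at about minute 0 and is counted. Reactions that end the infusion should surface in the discontinuation outputs. Both points stand. They reduce the likely effect, but the special-interest table would still not show those reactions beside the others.

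Third, the listing is probably sound. It states no window, and its most natural reading is a treatment-emergent event with a listed term, which includes onset during infusion. That also stands, so the point concerns the table.

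A reader might go further in three directions that the documents do not support:
- That these events vanish from safety reporting or from the IDMC. Step 5 of the working shows that they do not.
- That the earlier phase 3 trial proves such events occur during infusion. Protocol 2.1.5 reports 6 versus 0 serious hypotension events "immediately (within 2 hours) following the administration of nerinetide", without onset times, so it does not show that any began while the drug was running.
- That the excluded minutes measure the loss. For a 10-minute infusion they are 10 of 130, or 7.7% of the clock time from start of infusion to 120 minutes after its end. That is a share of time and says nothing about the share of events.

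**Conclusion.** The point holds as a minor defect of definition. On a literal reading of SAP 7.1, a listed reaction with onset before the end of infusion is excluded from the special-interest summary table, and one that causes the infusion to be stopped is always excluded. This conflicts with the treatment-emergence rule in SAP 1.8 and works against the table's purpose.

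The effect is limited to one descriptive table. The main safety analyses (serious adverse events and 90-day mortality) and the five IDMC safety tables are unaffected. How many events would be missed is unknown and could be none. The conclusion assumes that the table is programmed as written and that onset is dated to when the reaction began.

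**What to change.** In SAP 7.1, define special-interest onset, for both the table and the listing, as from the start of study drug infusion through 120 minutes after its end or early termination. This agrees with SAP 1.8 and is compatible with protocol 8.3. Stating it for the listing as well removes any doubt about whether the table's window carries over. Flagging events that began during infusion is optional.

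The cost is one phrase in the SAP and one line of derivation code. SAP 5.3 already summarises infusion duration, and SAP 1.8 already compares event start with dosing time, so no new data are needed. The wording of protocol 8.3 can be aligned at the next amendment and does not need one of its own. Making the change before unblinding avoids redefining a safety table after results are known. It alters a reporting definition only and leaves clinical management untouched.
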